SECONDARY ENDPOINTS	Secondary outcomes will include feasibility of providing medication abortion with drugs dispensed by mail-order pharmacy, clinical effectiveness and safety of medication abortion with drugs dispensed by mail-order pharmacy, and provider acceptability of the mail-order pharmacy model for dispensing medication abortion drugs. Feasibility will be assessed by measuring the proportion of patients who receive the medications by Day 2 and by Day 3 and whether patients’ confidentiality is maintained when they receive the medications by mail. We will also ask patients whether the medications were lost, stolen or damaged, resulting in the patients needing to return to clinic, or go elsewhere. We will also assess feasibility through open-ended interviews with providers of MA at the end of the study. Clinical effectiveness and safety will be assessed through analysis of electronic health record data, including the proportion of patients who experience a complete abortion and experience complications, including adverse events, related to the abortion. Provider acceptability will be assessed qualitatively through open-ended interviews with providers and staff involved in the study. We will identify advantages and disadvantages of mailing the medications from the perspective of providers and staff.
OTHER EVALUATIONS	N/A
SAFETY EVALUATIONS	Data abstraction of medical records will provide clinical data for analysis, including the proportion of patients who

	experience a complete abortion. We will conduct quantitative analyses of clinical data and the PI will track all reports of adverse events and serious adverse events to monitor safety.
PLANNED INTERIM ANALYSES	No formal interim analysis is planned. Serious and unexpected adverse events will be monitored on an ongoing basis throughout the study.
STATISTICS Primary Analysis Plan	We will use descriptive analyses using chi-square and t tests where appropriate to assess patient satisfaction with the model and clinical outcomes of patient participants.

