### 16.3 Analysis of Primary Endpoint

Acceptability and satisfaction with the mail-order model among patients will be assessed through patient surveys, which will include some open-ended items. The particular variables we will analyze include those on overall satisfaction with the medication abortion service (including whether they would use this mail-order medication abortion service again if they needed another abortion, and whether they would recommend the service to a friend), satisfaction with receiving the medications by mail, reasons for dissatisfaction (open ended questions), and perceptions about the wait time to receive the medications. We will also analyze the reasons why patients who decline participation in the study report not being interested in receiving the medications by mail, as indicated in close-ended and open-ended responses.

We plan to recruit for the main study a minimum sample of 440 participants and a maximum of 625 patients. With the addition of 25 patients in the pilot study, the target minimum number of patients recruited for the study is 465 and the maximum number is 650.

The sample size calculation for this study is based on two measures of acceptability: the proportion of patients who report they would use medication abortion again if they needed another abortion and the proportion who report they were “satisfied” or “very satisfied” with the medication abortion. For both power calculations, we assume 10% loss to follow up, 10% adjustment for clustering, a 5% non-inferiority margin, and a two-sided alpha of 0.05. Research with patients obtaining clinic-based medication abortion has estimated the proportion who would use medication abortion again as 89.7% (Teal, Dempsey-Fanning et al. 2007). Based on our assumptions, with a minimum sample of 440 patients, we will have a final analytic sample of approximately 400 patients, which gives us 79% power to assess this measure of acceptability; with a maximum sample of 625 recruited patients, we will have a final analytic sample of approximately 560 patients, which gives us 92% power.

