## 16.4 Analysis of Secondary Endpoints

Feasibility of the mail-order pharmacy dispensing model will be assessed through surveys with patients, and include determination of the proportion of patients who receive the medications by Day 2 and by Day 3 after the prescription is sent, the quality of the packaging, whether patient confidentiality was compromised due to receiving the medications by mail, as well as the proportion of patients who had to go to the clinic to obtain the medications.

Clinical effectiveness and safety outcomes, including adverse events, with medication abortion obtained via mail-order pharmacy will be assessed using quantitative data abstracted from patient medical records, as well as information on clinical outcomes captured in the Day 14 patient survey. The analysis populations for the effectiveness and safety endpoints will include patients who enroll in the study, take either of the medications, and for whom we have follow-up data. We will not assume that patients who do not have follow-up data had a successful abortion.

Effectiveness will be defined as the successful completion of abortion (versus incomplete abortion or continuing pregnancy), without vacuum aspiration. Continuing pregnancy will be defined as a viable pregnancy following treatment and need for vacuum aspiration to terminate the pregnancy or cases where a patient elects to continue the pregnancy after failed treatment (Creinin & Chen 2016). We will document vacuum aspiration abortions, including reasons for aspiration, reported by participants and those determined as necessary by the study providers at follow-up visits. We will compare effectiveness (the proportion of our sample that experiences a complete abortion not requiring vacuum aspiration) with published estimates (97.4%) (FDA 2016), using an exact binomial test. Assuming 10% loss to follow-up and 10% adjustment for clustering, and a two-sided alpha of 0.025 (to account for type I error), we estimate that a final analytic sample ranging from approximately 400 to 560 patients gives us 98% to 100% power to determine that mail-order medication abortion is as effective as in-person dispensing, if effectiveness in the mail-order model is no lower than 92.4%. A non-inferiority limit is defined as -5% and as an acceptable difference in the proportion of complete abortions.

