## 16.6 Sample Size

In addition to the 25 patients in the pilot study, we aim to recruit a minimum of 440 and a maximum of 625 patients for this study, across 15-20 sites. The sample size calculation for this study is based on a measure of acceptability: the proportion of patients who report they would use medication abortion again if they needed another abortion. Research with patients obtaining clinic-based MA has estimated that proportion as 89.7% (Teal, Dempsey-Fanning et al. 2007). We would like to determine if acceptability of medication abortion when receiving the medications by mail is no more than 5% lower than 89.7%. Assuming 10% loss to follow-up, with a minimum sample of 440 patients, we will have a final analytic sample of approximately 400 patients; with a sample of 625 recruited patients, we will have a final analytic sample of approximately 560 patients. With a 2-sided alpha of 0.05 and 10% adjustment for clustering, a final analytic sample size of approximately 400 gives us 79% power, and an analytic sample of 560 gives us 92% power to assess this measure of acceptability.

We aim to interview all the providers (or staff administrators) involved in medication abortion provision at the study sites, up to 50. This sample size will be determined by the number of providers/staff at the study sites.

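### All power figures include a 10% allowance for clustering by site, but no planned analysis accounts for site; the effect is small at the plan's own 10% and larger only if within-site correlation is higher

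*Combined protocol and SAP*

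**What the plan says.** Clustering by site appears in every power statement:

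- Section 16.3, for both acceptability measures: "we assume 10% loss to follow up, 10% adjustment for clustering, a 5% non-inferiority margin", with a two-sided alpha of 0.05. Stated power is 79% and 92% for willingness to use the method again, and 77% and 90% for satisfaction, at about 400 and 560 analysed patients.
- Section 16.6: "With a 2-sided alpha of 0.05 and 10% adjustment for clustering, a final analytic sample size of approximately 400 gives us 79% power". The synopsis repeats this.
- Section 16.4, for effectiveness: "using an exact binomial test. Assuming 10% loss to follow-up and 10% adjustment for clustering, and a two-sided alpha of 0.025". Stated power is 98% to 100% against a bound of 92.4%, which is 5 points below 97.4%.

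The analyses are described as follows:

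- Effectiveness (16.4): an exact binomial test.
- Acceptability (16.3): a list of variables, with no test or interval.
- Synopsis, primary analysis plan: "We will use descriptive analyses using chi-square and" t tests.

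Section 5 plans 15-20 sites. The documents contain no ICC, site effect, design-effect correction, mixed model or cluster-robust variance. The opening of Section 16 promises a detailed SAP that may modify the analysis, but the documents contain no cluster method from it.

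**The concern.** The sample size treats patients at one site as correlated. The one inferential test that is named treats them as independent, and for acceptability the method is left open. The plan therefore states power for one kind of analysis and specifies another, or none.

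The direction matters because non-inferiority is judged against a fixed bound. A variance that is too small moves the implied lower limit up and favours the claim. Site differences are plausible. Section 5 allows newly trained ob/gyn, family medicine and internal medicine clinics alongside current abortion providers. Section 10.3 offers several follow-up methods and leaves the management of ongoing pregnancy to each site's practice, which can affect aspiration and so the effectiveness endpoint.

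**Working it through.** **Inputs.** Analysed n of 400 and 560 (16.3, 16.4, 16.6). These already reflect 10% loss: 440 x 0.9 = 396 and 625 x 0.9 = 562. The clustering allowance must therefore enter as a further reduction. Read as a design effect of 1.1, it gives 400/1.1 = 364 and 560/1.1 = 509. One-sided alpha is 0.025 for acceptability and 0.0125 for effectiveness. Bounds (p0) and assumed rates (p1) are 84.7% and 89.7% (use again), 83.4% and 88.4% (satisfaction), and 92.4% and 97.4% (effectiveness).

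**1. Reproducing the stated power.** For acceptability, the one-sample score formula: power = Phi{[(p1 - p0) - 1.96 sqrt(p0(1 - p0)/n)] / sqrt(p1(1 - p1)/n)}. For effectiveness, the exact binomial: the smallest r with P(X >= r | p0) <= 0.0125, then P(X >= r | p1).

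| Measure | Stated | n = 364 / 509 | n = 400 / 560 |
|---|---|---|---|
| Use again | 79% / 92% | 79.3% / 91.8% | 83.4% / 94.2% |
| Satisfaction | 77% / 90% | 75.8% / 89.4% | 80.1% / 92.2% |
| Effectiveness | 98% to 100% | 98.4% / 99.9% (r = 348, 484) | 99.0% / 99.95% (r = 382, 532) |

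The reduced sample matches exactly or within about 1 point.

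**2. ICC implied by 10%.** DEFF = 1 + (m - 1) x ICC, where m is patients per site. The smallest m is 400/20 = 20, giving 0.1/19 = 0.005. The largest is 560/15 = 37.3, giving 0.1/36.3 = 0.003.

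**3. Consequence at the plan's own design effect.** The correct standard error is sqrt(1.1) = 1.049 times the independent-patient one.

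- Exact effectiveness test, nominal one-sided 1.25%: the actual rate under independence is 0.87% (n = 400) and 0.94% (n = 560), because the test is discrete. With 15-20 equal sites and beta-binomial site counts, convolved exactly, it rises to about 1.1% and 1.2%.
- Acceptability, if a normal-approximation test were used: 1 - Phi(1.96/sqrt(1.1)) = 1 - Phi(1.869) = 3.1% against 2.5%. If an exact test were used: 2.3-2.7%.

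**4. Consequence at larger ICCs.** These values are assumptions; the documents give none. One-sided false-claim rates of unadjusted exact tests, over 15-20 equal sites and n = 400 to 560:

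| Assumed ICC | Effectiveness (nominal 1.25%) | Acceptability (nominal 2.5%) |
|---|---|---|
| 0.01 | 1.4-2.1% | 2.7-4.1% |
| 0.02 | 2.1-3.6% | 3.7-6.2% |

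**5. Information about clustering in the effectiveness data.** Expected failures at 97.4% success are 400 x 0.026 = 10.4 and 560 x 0.026 = 14.6, or fewer than one per site.

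**The case against.** The strongest reply is that the mismatch has almost no practical effect at the assumption the plan makes. Most of that stands:

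- The exact effectiveness test stays at or below its nominal level at a design effect of 1.1.
- The stated power is not inflated. On independent patients the exact test has 99.0% and 99.95% power, and with clustering at a design effect of 1.1 about 98.7% and 99.9%. Both are in line with 98% to 100%. An unadjusted exact test of the use-again measure has 81.0% and 93.1% under independence, slightly above the stated figures.
- The match to n/1.1 is not unique. Taking n x 0.9 (360 and 504) gives 78.8% and 91.5% for use-again, almost the same.
- Section 16.3 has no test that ignores clustering. Its gap is an unnamed method.
- Section 16.4 names a test rather than a confidence limit, so any limit discussed here is the one that test implies.

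The promise of a later SAP does not close the gap. It shows where the repair can go, but no cluster method is stated, and one chosen after outcomes are known would be a discretionary choice in a comparison with historical figures.

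A reader might infer that larger ICCs are likely because the sites differ in kind. The documents make variation plausible but give no basis for its size.

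**Conclusion.** The inconsistency is real: clustering is in every power figure and in no planned analysis. At the plan's own 10% it is worth about 5% on the standard error and leaves the exact effectiveness test near its nominal level. Material inflation needs an ICC of about 0.01 or more, above the 0.003-0.005 that 10% implies.

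Two stronger readings are not supported. The first is that the effectiveness test as written exceeds its alpha under the plan's assumptions; the exact calculation gives 1.1-1.2% against 1.25%. The second is that true power for the use-again measure falls to one lower figure. A t critical value on sites minus one with the null variance gives about 73-75% and 88-89%, while a Wald limit with estimated variance gives about 83-84% and 93-94%. Restated power depends on the method, and none is named.

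These results assume that the 10% is a design effect of 1.1, that sites are equal in size, that site counts are beta-binomial, and that effectiveness is decided against 92.4%. This should be corrected, but it does not undermine the design.

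**What to change.** In Sections 16.3 and 16.4, or in the promised SAP before outcome data are seen:

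1. Base the non-inferiority decision for effectiveness and both acceptability measures on a cluster-adjusted lower limit. The simplest is Clopper-Pearson on n/DEFF, with DEFF no lower than 1.1.
2. For effectiveness, fix DEFF at 1.1. This keeps the stated power (98.4% and 99.9%). Report an estimated DEFF, or a GEE with site-robust variance, only as a sensitivity analysis, because 10-15 failures over 15-20 sites make such estimates unstable.
3. For acceptability, report the estimated ICC and use the larger of the estimated DEFF and 1.1.
4. State the ICC behind the 10% and its basis.
5. Restate acceptability power only for the method chosen. With the exact limit at a DEFF of 1.1 it is 80.8% and 90.5% for use-again (r = 322 of 364 and 448 of 509), and 76.1% and 87.8% for satisfaction (r = 318 and 442). An estimated DEFF above 1.1 would lower these.

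The cost is wording and standard software, slightly wider limits and possibly slightly lower stated power.

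### Section 16.4 attaches its 98% to 100% power to any true effectiveness from 92.4% up, but 92.4% is the non-inferiority limit, where the chance of success is about 1%; the figure holds for a true rate near 97.4%

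*Combined protocol and SAP*

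**What the plan says.** Section 16.4 defines effectiveness as complete abortion without vacuum aspiration and compares the observed proportion "with published estimates (97.4%) (FDA 2016), using an exact binomial test". The error rate is "a two-sided alpha of 0.025 (to account for type I error"), with allowances described as "Assuming 10% loss to follow-up and 10% adjustment for clustering". On that basis "a final analytic sample ranging from approximately 400 to 560 patients gives us 98% to 100% power", described as "power to determine that mail-order medication abortion is as effective as in-person dispensing, if effectiveness in the mail-order model is no lower than 92.4" per cent. The next sentence reads: "A non-inferiority limit is defined as -5% and as an acceptable difference in the proportion of complete abortions".

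The section names 97.4% as the published comparator and 92.4% as the lowest effectiveness for which the power is claimed. It does not say which true rate the power was computed at, which rate is the null hypothesis, or what result would count as success.

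**The concern.** The limit of -5 points applied to 97.4% gives 92.4%. In a non-inferiority test that value is the null boundary, so a true rate of 92.4% must lead to a positive conclusion no more often than the type I error allows. The sentence instead makes 92.4% the floor above which power is 98% or more. No test that controls its error rate at 92.4% can have that property.

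The consequence is for interpretation. The plan calls a shortfall of up to 5 points acceptable and, as worded, promises near-certain confirmation across that whole range. If the true rate were 94% or 95%, a failure to exclude 92.4% would be a common result. With 98% power on record, it could be misread as evidence against mail-order dispensing. Section 16.4 contains the plan's only power statement for effectiveness, and section 2 says that the results could eventually bear on the REMS.

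**Working it through.** **Inputs (section 16.4 unless noted)**
- Published rate 97.4%; limit 97.4% − 5 = 92.4%.
- One-sample exact binomial test in a single cohort.
- Two-sided alpha 0.025. Assumption: 0.0125 is spent in the non-inferiority direction.
- Analysed n about 400 to 560. Section 16.6 shows that this is already net of loss to follow-up: 440 × 0.9 = 396 and 625 × 0.9 = 562.5.
- Clustering adjustment 10%. Assumption: applied as n/1.1, so 400/1.1 ≈ 364 and 560/1.1 ≈ 509.

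**Formula.** With X the number of complete abortions, r is the smallest count for which P(X ≥ r | n, 0.924) ≤ 0.0125. Power at a true rate p is P(X ≥ r | n, p) = Σ C(n,k) p^k (1−p)^(n−k), summed over k = r, …, n.

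**Step 1: reproduce the printed figure.** The critical counts are r = 348 of 364 and r = 484 of 509. At p = 0.974, power is 98.4% and 99.9%, which matches 98% to 100%.

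**Step 2: apply the condition that the plan states.** At p = 0.924 the same test succeeds with probability 0.95% and 1.03%. The last two columns below repeat the calculation with 0.025 spent in one direction (r = 347 of 364 and 483 of 509).

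| True rate | 0.0125, n 364 | 0.0125, n 509 | 0.025, n 364 | 0.025, n 509 |
|---|---|---|---|---|
| 92.4% | 1.0% | 1.0% | 1.7% | 1.7% |
| 94% | 12% | 17% | 17% | 23% |
| 95% | 35% | 52% | 45% | 60% |
| 96% | 71% | 88% | 79% | 91% |
| 97% | 95% | 99% | 97% | >99% |
| 97.4% | 98.4% | 99.9% | 99.2% | >99.9% |

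At one-sided 0.0125, power of 98% is reached from a true rate of about 97.3% at the minimum sample and 96.7% at the maximum. Power of 80% is reached from about 96.3% and 95.7%.

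**Step 3: drop the clustering adjustment.** With n = 400 and 560, r is 382 and 532. Success then needs at most 18 or 28 failures, that is, an observed rate of at least 95.5% or 95.0%. Power is 0.9% and 0.9% at 92.4%, 38% and 55% at 95%, and 99.0% and 99.95% at 97.4%. The pattern is the same.

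**Step 4: a second calculation that gives the same figure.** Take the null as 97.4%, reject in the lower tail at 0.0125, and set the true rate at 92.4%. The test rejects at 346 or fewer successes of 364, or 486 or fewer of 509, and power is 98.3% and 99.8%. This too matches 98% to 100%, but rejecting here means concluding that mail-order is below 97.4%.

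The two tests can both be significant on the same data. With 560 independent patients, 532 to 535 successes exclude 92.4% and are also significantly below 97.4%. So the plan needs to say which test carries the conclusion.

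**The case against.** The best defence is that a reader used to non-inferiority designs will take the 92.4% clause as a loose statement of the success criterion, with power computed at equality with the comparator, as is usual. On that reading the figure is correct. It stands that the arithmetic is sound and that the fault lies in the stated condition. But the sentence makes 92.4% a condition on how effective the mail-order model is, and gives no other true rate. Even the lenient reading leaves the assumed rate unstated.

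A second defence is that the test literally named compares with 97.4%, so 92.4% is the alternative and power there really is about 98% (step 4). The documents do not show which calculation was run, so this cannot be excluded. It does not rescue the sentence, because it is power to find mail-order worse, and failing to find that does not establish that it is as effective.

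A third point is fair. Effectiveness is a secondary endpoint, the sample size was set on acceptability, and section 16 provides for a detailed SAP before the final analysis. This limits the weight of the issue but does not remove it.

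**Conclusion.** The power statement is wrong as worded and should be corrected. At the rate it names, the chance of concluding non-inferiority is about 1%, or 1.7% if 0.025 is spent in one direction. The claimed 98% to 100% is right for a true effectiveness of 97.4%. The intermediate figures rest on two readings that the plan does not spell out: how alpha is divided and how clustering is applied. At 95% they run from 35% to 60% across both alpha readings and both sample sizes, and at 96% from 71% to 91%. The conclusion does not depend on either choice.

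A reader might infer more than the documents support:
- That the power exists only at exactly 97.4%. It does not: at 97% it is already 95% to 99%.
- That the printed number can come only from assuming 97.4%. Step 4 gives it another way.
- That a true 95% would usually fail. This holds at the minimum sample under either alpha reading, but at the maximum sample success is about even or slightly better. At 94% failure is likely for both samples.
- That the study is too small. The sample size does not rest on this endpoint, and nothing here calls for more patients.

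**What to change.** Revise the power sentence in section 16.4, and carry the change into the SAP that section 16 promises:
- State that the test is against a null of 92.4%, and that non-inferiority is concluded if the lower confidence limit for effectiveness exceeds 92.4%.
- State that the 98% to 100% power assumes a true effectiveness of 97.4%.
- Add the power at true rates of 95% and 96%, naming the alpha and clustering assumptions: 35% to 52% and 71% to 88% with 0.0125 in the non-inferiority direction and n/1.1, or 45% to 60% and 79% to 91% if 0.025 is spent in one direction.
- Replace the claim of being as effective with the claim that effectiveness is less than 5 percentage points below the published 97.4%.

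If the sponsor in fact powered a test of 97.4% against 92.4%, it should say so and not present that figure as power to show non-inferiority.

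The cost is a few sentences and a less favourable stated power for true rates below about 97%. Recruitment targets, data collection and the primary analysis do not change.
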